### 8.4.2 Day of Surgery (Visit 2, Day 0)

## **The SPENCER Study**

---

At the Day of Surgery (Visit 2, Day 0), the following assessments will be performed:

- Prior and concomitant medication
- AEs (record incidence and severity of any adverse events that occur after the insertion)
- CE/PCIOL
- DEXTENZA insertion
- Indicate number of attempts to successfully insert DEXTENZA
- Insert visualization
- Record phacoemulsification time
- Indicate the incision type, location, and size (mm)
- Prescribe post-operative topical therapy regimen – No topical NSAID's
- Physician ease of insertion and visualization

### **8.4.3 Post-Operative Day 1 (Visit 3, Day 1)**

At the Day after Surgery (Visit 3, Day 1), the following assessments will be performed:

- Prior and concomitant medication
- AEs (record incidence and severity of any adverse events that occur after the insertion)
- Distance visual acuity (VA)
- Ocular pain assessment (0 to 10)
- Slit lamp examination (including anterior chamber count and anterior chamber flare)
- Insert visualization

### **8.4.4 Post-Operative Day 8 (Visit 4, Day 8) Day 14 (Visit 5, Day 14) and Day 30 (Visit 6, Day 30)**

At the Day 8, Day 14 and Day 30 Visits, the following assessments will be performed:

- Prior and concomitant medication
- AEs (record incidence and severity of any adverse events that occur after the insertion)
- Distance visual acuity (VA)
- Best-Corrected Visual Acuity
- Ocular pain assessment (0 to 10)
- Slit lamp examination (including anterior chamber count and anterior chamber flare)
- Intraocular pressure
- Insert visualization

- MAC OCT Day 30
- Dry eye severity as measured by VAS on Day 8 and Day 30

## 9 ADVERSE EVENTS

The Investigator and study staff are responsible for detecting and recording AEs and serious adverse events (SAEs), during scheduled safety evaluations and whenever such information is brought to their attention.

This section of the protocol provides definitions and detailed procedures to be followed.

During each visit, the Investigator will question the subject about AEs using an open question, taking care not to influence the subject's answers. Throughout the course of the study, every effort must be made to remain alert to possible AEs. If an AE occurs, the first concern should be for the safety of the subject. If necessary, appropriate medical intervention should be provided. At the signing of the ICF, each subject must be given the names and telephone numbers of study site staff for reporting AEs and medical emergencies.

### 9.1 Definition of an Adverse Event

An AE is any untoward medical occurrence in a subject or clinical investigation subject administered a pharmaceutical product and that does not necessarily have a causal relationship with this treatment. An AE can therefore be any unfavorable and unintended sign (including an abnormal laboratory finding), symptom, or disease temporally associated with the use of a medicinal (investigational) product, whether or not related to the medicinal (investigational) product. Examples of an AE include:

- Exacerbation of a pre-existing condition including either an increase in frequency and/or intensity of the condition.
- New conditions detected or diagnosed after DEXTENZA administration even though it may have been present prior to the start of the study.
- Signs, symptoms of a drug interaction.
- Signs, symptoms of a suspected overdose of DEXTENZA or a concurrent medication (overdose per se should not be reported as an AE/SAE).

### 9.2 Definition of Serious Adverse Event

A SAE is any untoward medical occurrence that at any dose:

- Results in death
- Is life-threatening

**Note:** The term "life-threatening" refers to an event in which the subject was at risk of death at the time of the event; it does not refer to an event which hypothetically might have caused death if it were more severe.

- Requires in-patient hospitalization or prolongation of existing hospitalization. Hospitalizations for elective surgeries do not constitute a SAE
- Results in persistent or significant disability/incapacity
- Is a congenital abnormality/birth defect

## **The SPENCER Study**

---

Medical and scientific judgment should be exercised in deciding whether other situations should be considered SAEs, such as important medical events that might not be immediately life-threatening or result in death or hospitalization but might jeopardize the subject or might require intervention to prevent one of the other outcomes listed above.

### **9.3 Disease-Related Events or Outcomes Not Qualifying as AE/SAEs**

Not applicable.

### **9.4 Monitoring and Recording of AEs and SAEs**

#### **9.4.1 Adverse Events**

Any AE experienced by the subject from the Screening/Baseline Visit after insertion of the DEXTENZA, through the 29-Day PostInsertion Visit is to be recorded in the CRF, regardless of the severity of the event or its relationship to study treatment.

Any AEs already documented at a previous assessment and designated as ongoing should be reviewed at subsequent visits, as necessary. If these have resolved, this should be documented.

Changes in intensity or frequency of AEs should be recorded as separate events (i.e., a new record started).

#### **9.4.2 Serious Adverse Events**

Any SAE experienced by the subject from the Screening/Insertion Visit through the 29-Day Post-Insertion Visit is to be recorded on a SAE Form, regardless of the severity of the event or its relationship to study treatment.

Any SAE ongoing when the subject completes the study or discontinues from the study will be followed by the Investigator until the event has resolved, stabilized, or returned to baseline status.

#### **9.4.3 All Events**

All events must be assessed to determine the following:

- If the event meets the criteria for a SAE as defined in Section 9.2
- The severity of the event as defined in Section 9.7.1
- The relationship of the event to study treatment as defined in Section 9.7.2

### **9.5 Immediate Reporting of Serious Adverse Events and Pregnancies**

In order to adhere to all applicable laws and regulations for reporting a SAE or pregnancy, the study site must formally notify the pharmacovigilance team within 24 hours of the study site staff becoming aware of the SAE. It is the Investigator's responsibility to ensure that the SAE is emailed or faxed as described in Figure 3. It may be necessary for the pharmacovigilance team to directly communicate with the Investigator if additional information is required.

#### **Figure 3 Reporting Information for SAEs and Pregnancies**

To report initial or follow up SAE information email or fax a copy of the SAE or Pregnancy report form to the following:

**ProPharma Group**

Email: [[contact]](mailto:[contact])

[contact]

[contact]

After the initial SAE report, the Investigator is required to proactively follow each subject and provide further information to the pharmacovigilance team on the subject's condition within 24 hours. New or updated information will be recorded on the SAE reporting form. The updated SAE reporting form should be sent to the pharmacovigilance team within 24 hours as described in Figure 3.

All additional follow-up evaluations must be reported to the pharmacovigilance team. Such data should be sent by fax or email (Figure 3) within 10 calendar days. All SAEs will be followed until the Investigator and Ocular Therapeutix agree that the event is satisfactorily resolved.

## 9.6 Death

The death must be recorded on the appropriate CRF. All causes of death must be reported as SAEs. The Investigator should make every effort to obtain and send death certificates and autopsy reports to the pharmacovigilance team.

## 9.7 Evaluating AEs and SAEs

### 9.7.1 Severity

The following definitions should be considered when evaluating the severity of AEs and SAEs.

**Mild** Event is noticeable to the subject but is easily tolerated and does not interfere with the subject's daily activities.

**Moderate** Event is bothersome, possibly requiring additional therapy, and may interfere with the subject's daily activities.

**Severe** Event is intolerable, necessitates additional therapy or alteration of therapy, and interferes with the subject's daily activities.

For AEs that change in intensity, the start and stop date of each intensity should be recorded.

An AE that is assessed as severe should not be confused with a SAE. An event is defined as 'serious' when it meets one of the pre-defined outcomes as described in Section 9.2

### 9.7.2 Relationship to Investigational Procedure

The following definitions should be considered when evaluating the relationship of AEs and SAEs to the study treatment:

**Unrelated** This category applies to those (S)AEs which, after careful consideration, are clearly and incontrovertibly due to extraneous causes (disease, environment, etc.); there is no reasonable probability that the (S)AE may have been caused by the procedure or the product. If the Investigator determines that the AE is unlikely to be related to the study drug or procedure, then this would be the appropriate category.

**Related** The following criteria should be applied in considering inclusion of a (S)AE in this category:

- a. It bears a reasonable temporal relationship to the procedure or the presence of DEXTENZA.
- b. It could not be reasonably explained by the known characteristics of the subject's clinical state, environmental or toxic factors, or other factors (e.g., disease under study, concurrent disease(s), and concomitant medications) and modes of therapy administered to the subject
- c. It disappears or decreases on removal of the IP
- d. It follows a known pattern of response to the procedure or the product

### 9.7.3 Expectedness of Events

Expectedness of all AEs will be determined according to the Investigator's Brochure as determined by Ocular Therapeutix, Inc.

### 9.7.4 Clarifications

The following definitions should be considered when evaluating the relationship of AEs and SAEs to the study treatment:

**Hospitalization** Hospitalization for the elective treatment of a pre-existing condition (i.e., a condition present prior to the subject's signature of the informed consent) that did not worsen during the study is not considered a SAE. Complications that occur during hospitalization are AEs. If a complication prolongs hospitalization or meets any of the other SAE criteria, the complication is a SAE.

**Pre-existing Conditions** Pre-existing conditions (i.e., conditions present or detected at the start of the study) which worsen during the study, exacerbation of a pre-existing illness or an increase in frequency or intensity of a pre-existing episodic event or condition are (S)AEs. Anticipated day-to-day fluctuations of pre-existing condition(s) that do not worsen with respect to baseline are not (S)AEs.

**Medical or Surgical Procedure** Medical or surgical procedures (e.g., colonoscopy) are not (S)AEs; however, the condition that leads to the procedure may be considered a (S)AE.

In the case of elective medical or surgical procedures, or pre-study planned medical or surgical procedures for pre-existing conditions (i.e., a condition present prior to the subject's signature of the ICF) that did not worsen during the study the condition that leads to the procedure does not need to be reported as a (S)AE.

**Death** Death is not a SAE; the condition that leads to the death is a SAE.

**Abnormal Laboratory Value** In the absence of a diagnosis, abnormal laboratory values that are judged by the Investigator to be clinically significant must be recorded as a (S)AE. Clinical significant abnormal laboratory findings that are present at baseline and significantly worsen following the start of the study will also be reported as a

(S)AE.

## **9.8 Pre-scheduled or Elective Procedures or Routinely Scheduled Treatments**

A pre-scheduled or elective procedure or routinely scheduled treatment will be allowed at the investigators discretion.

## **9.9 Procedures for Handling Special Situations**

### **9.9.1 COVID-19 Pandemic**

In response to the coronavirus disease 2019 (COVID-19) pandemic, study visits and procedures/assessments should be conducted in accordance with the protocol if at all possible. If a subject is unable to attend a scheduled study visit in the per-protocol timeframe due to COVID-19 restrictions, visit windows may be extended to accommodate subject availability. Alternatively, if a subject is unable to attend a study visit in-person due to COVID-19 restrictions, a televisit should be conducted (if possible) in accordance with the visit schedule, with a focus on completion of safety assessments.

### **9.10 Pregnancy**

Not applicable. Age limitation will exclude the possibility of pregnancy.

### **9.10.1 Regulatory Reporting**

Suspected unexpected serious adverse reactions (SUSARs) are SAEs that are unexpected and judged by the Investigator or Ocular Therapeutix to be associated to the study treatment administered. Ocular Therapeutix will report SUSARs to the appropriate authorities within the required regulatory timeframes. Reports of SUSARs will be made to Institutional Review Board (IRBs)/Independent Ethics Committee (IEC) and Investigators, as needed.

## **10 STATISTICAL METHODS AND DATA ANALYSIS**

### **10.1 Statistical Methods**

This study is designed to be descriptive in nature; therefore, there will be no formal statistical analyses completed. There will be a general statistical analysis plan (SAP) that will briefly summarize how the data will be presented. Summaries for continuous variables will include the sample size, mean, standard deviation, median, minimum and maximum. Summaries for discrete variables will include frequencies and percentages.

### **10.2 Sample Size Determination**

No formal sample size calculations were performed.

### **10.3 Statistical Significance**

There will be no formal statistical analyses performed. All summaries will be descriptive in nature.

### **10.4 Subject Population for Analysis**

Subjects undergoing non-complicated CCI CE/PCIOL in one or both eyes with or without iStent/Hydrus/Goniotomy. All safety and efficacy analyses will be performed on the safety population.

## 10.5 Demographics and Baseline Data

Subject disposition will be presented, including the number of subjects screened, enrolled, and treated. The number of subjects who completed the study and reasons for discontinuation will be summarized.

Demographic and baseline characteristics (including medical history) will be summarized.

## 10.6 Primary Efficacy Analysis

The primary efficacy endpoints are:

- Absence of anterior chamber cells at Day 14 as measured by Summed Ocular Inflammation Score (0 to 4)
- Absence of ocular pain at Day 8 as measured by ocular pain assessment numerical grading scale (0 to 10)

Anterior chamber cells and ocular pain will be summarized using descriptive statistics (n, mean, standard deviation, median, minimum, and maximum).

## 10.7 Secondary Efficacy Analysis

Secondary Efficacy Endpoints are

- Mean change in BCVA from Baseline
- Number and percentage of subjects with complete absence of pain
- Number and percentage of subjects with complete absence of cell
- Measuring cell, pain, and flare on Day 8,14,30
- Physician ease of insertion and visualization
- Number of attempts to successfully insert Dextenza
- Dry eye severity as measured by VAS at baseline, Day 8 and Day 30
- Record insert retention up to 30 days

Mean change in BCVA from baseline will be summarized using descriptive statistics (n, mean, standard deviation, median, minimum, and maximum).

The number and percentage of subjects with complete absence of pain and with complete absence of cell will be summarized.

The number and percentage of investigators' responses to ease of insertion and visualization (easier, the same, and more difficult) will be summarized.

The number of attempts to successfully insert DEXTENZA will be summarized.

Dry eye severity as measured by VAS will be summarized using descriptive statistics (n, mean, standard deviation, median, minimum, and maximum).

Insert retention as measured by yes or no will be summarized.

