## **5 TRIAL OBJECTIVES**

The study objectives are to evaluate the safety and effectiveness of treatment with an intracanalicular dexamethasone (0.4mg) insert in the operating room following cataract surgery/intraocular lens implant (IOL) with or without iStent/Hydrus/Goniotomy when placed in the lower punctum compared to the upper punctum.

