### **6.3 Randomization and Masking ✓**

This is an open-label study. All subjects will receive DEXTENZA. Subjects will be randomized to one of two treatment groups. Group 1 will receive the insert in the lower punctum on the day of surgery in the OR and Group 2 will receive the insert in the upper punctum on the day of surgery in the OR.

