### Appendix 3    VAS for Eye Dryness

The following procedures should be followed for conducting the study assessments. The Visual Analog Scale (VAS) should be performed prior to all other ocular assessments.

To complete the VAS questionnaire, ask the subject to rate the severity and the frequency of symptom of eye dryness (0%-100%) by placing a vertical mark (|) on the horizontal line to indicate the level of eye discomfort that they are experiencing in both eyes currently (i.e., right now) and how often the eye dryness is experienced.

0% corresponds to: "no discomfort"

100% corresponds to: "maximal (the most) discomfort"

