## 8.4 Study Assessment by Visit

### 8.4.1 Screening/Baseline Visit (Visit 1, Day -21 to -1)

At the Screening/Insertion Visit (Visit 1, Day -1), the following assessments will be performed. Ocular assessments will be performed in each eye:

- Informed consent
- Inclusion/exclusion criteria
- Demographics
- Medical and ocular history
- Prior and concomitant medications (record any medication that subject is taking as well as those taken in the previous 60 days)
- AEs (record incidence and severity of any adverse events that occur after the insertion)
- Distance VA
- Best-Corrected Visual Acuity
- Ocular pain assessment (0-10)
- Slit Lamp Examination (including anterior chamber cell count, and anterior chamber cell flare)
- Punctum examination (size and presence of any punctal plug)
- Grade cataract density (scale 1 to 4)
- Intraocular pressure
- Dilated fundus exam
- IOL measurement
- MAC OCT
- Dry eye severity as measured by VAS

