### **10.8.2 IOP**

The observed values and change from baseline values for IOP will be summarized by visit.

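### Dry-eye VAS is collected at baseline, but section 10.7 plans neither change from baseline nor a baseline-adjusted group difference, so a lower-versus-upper comparison is less precise than it need be

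*Combined protocol and SAP*

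**What the plan says.** Section 10.7 lists the endpoint as "Dry eye severity as measured by VAS at baseline, Day 8 and Day 30". Sections 8.4.1 and 8.4.4 schedule the measurement at those three visits. The analysis sentence for it in section 10.7 is "Dry eye severity as measured by VAS will be summarized using descriptive statistics (n, mean, standard deviation, median, minimum, and maximum", and nothing further is said about VAS.

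Two other outcomes with the same baseline and follow-up structure are handled differently. For visual acuity, section 10.7 says "Mean change in BCVA from baseline will be summarized using descriptive statistics". For pressure, section 10.8.2 says "The observed values and change from baseline values for IOP will be summarized by visit".

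The objective in section 5 is comparative: the insert "when placed in the lower punctum compared to the upper punctum". Section 6.3 states "Subjects will be randomized to one of two treatment groups". Appendix 3 asks the subject to place a mark "to indicate the level of eye discomfort that they are experiencing in both eyes currently", so there is one VAS record per subject and not one per eye. The Synopsis plans 60 to 80 eyes, with up to 40 in each group. Sections 10.1 to 10.3 give no sample size calculation and plan no formal analysis.

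**The concern.** For VAS, the trial's question can be answered only by setting the two groups side by side at Day 8 and Day 30. The eligibility criteria do not select on dryness, so subjects may start from different scores. If only follow-up levels are compared, the part of each score that the subject's own baseline would predict stays in the comparison as noise. In one particular trial, part of any chance difference at baseline also stays in the follow-up difference.

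The baseline value that would remove this is already being collected. If its use is not fixed beforehand, raw levels, changes and adjusted differences all remain open choices once the data are seen.

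**Working it through.** The plan gives no SD, correlation, effect size or power for VAS, so there is no figure of its own to reproduce. The check asks what baseline adjustment would be worth.

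**Inputs from the protocol:** VAS scale 0 to 100 (Appendix 3); 60 to 80 eyes, up to 40 per group (Synopsis).

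**Assumptions:** equal groups; SD 25 points at both visits (range 20 to 30); r = 0.4 to 0.7; n independent subjects per group; normal approximation.

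**Formulas for the 95% half-width of the difference in mean follow-up VAS:**
- Raw levels: 1.96 × SD × √(2/n)
- Baseline-adjusted (ANCOVA): raw × √(1 − r²)
- Change score: raw × √(2 − 2r)
- Equivalent gain in subjects from ANCOVA: 1/(1 − r²) − 1

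**Raw levels.** With n = 40 and SD 25: 1.96 × 25 × √0.05 = 11.0 points (8.8 at SD 20, 13.1 at SD 30). With n = 30 and SD 25: 12.7 points.

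**Alternatives at SD 25:**

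| r | ANCOVA, n = 40 | ANCOVA, n = 30 | Equivalent extra subjects | Change score, n = 40 |
|---|---|---|---|---|
| 0.4 | 10.0 | 11.6 | 19% | 12.0 |
| 0.5 | 9.5 | 11.0 | 33% | 11.0 |
| 0.6 | 8.8 | 10.1 | 56% | 9.8 |
| 0.7 | 7.8 | 9.0 | 96% | 8.5 |

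ANCOVA is narrower than raw levels whenever r is not 0. The change score is narrower only when r exceeds 0.5, and wider below that.

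**Chance imbalance.** The baseline mean difference has standard error √(2/n) in SD units: 0.224 for n = 40 and 0.258 for n = 30. The probability that it exceeds 0.3 SD (7.5 points at SD 25) in either direction is 2 × [1 − Φ(0.3/√(2/n))], which is 18% for n = 40 and 25% for n = 30. The expected carry-over to follow-up is r × imbalance: 0.5 × 7.5 = 3.75 points, or 3.0 at r = 0.4 and 5.25 at r = 0.7.

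**Eyes and subjects.** These n are subjects, while the plan counts eyes. At the extreme, if every subject contributed both eyes, 80 eyes would be 40 subjects, 20 per group. The raw half-width would then be 1.96 × 25 × √0.1 = 15.5 points, and 15.5 × 0.866 = 13.4 after adjustment at r = 0.5. The absolute widths grow, but the proportional gain is unchanged.

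**The case against.** The strongest case against has four parts.

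- **The study is descriptive.** Sections 10.1 and 10.3 exclude formal analyses, the Synopsis speaks of displaying data overall where applicable, and no lower-versus-upper VAS contrast is written down. This stands in part: the missing by-group contrast is a wider matter than VAS. But change from baseline is itself descriptive and is already planned for BCVA and IOP, and an adjusted difference with an interval is estimation, not a test.
- **Baseline VAS will be reported anyway.** It is one of the endpoint's three time points. If results are shown by group, an imbalance would be visible, and the difference in mean change could be derived for complete cases. That is true, but display by group is not required, and visit-by-visit summaries do not give the SD of the within-subject change.
- **The wording fits the endpoint.** VAS is defined as levels at three visits and BCVA as a mean change, and section 10.1 leaves presentation to a general SAP. This stands: the analysis does not contradict the endpoint definition.
- **Randomisation protects the comparison.** This also stands. An unadjusted interval already allows for chance imbalance.

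A reader might infer that dryness differs widely between these patients before surgery, or that a baseline imbalance passes in full into the follow-up means. The documents give no VAS spread or correlation to support the first. On the second, only the fraction r carries over.

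**Conclusion.** The point holds as an avoidable loss of precision, and as an inconsistency with how BCVA and IOP are handled. It does not hold as bias: a reader might take the unadjusted comparison to be systematically distorted, but section 6.3 randomises the subjects.

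At SD 25 with 40 subjects per group, adjustment narrows the half-width by 1.0 point at r = 0.4 (11.0 to 10.0) and by 3.2 points at r = 0.7 (11.0 to 7.8). SD and r are assumptions, and the number of independent subjects may be smaller than the number of eyes. This is one of eight secondary endpoints in a descriptive study, so the consequence is modest; the change is worth making because the data are already collected.

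**What to change.** Replace the VAS sentence in section 10.7 with:

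> VAS dryness severity at baseline, Day 8 and Day 30, and change from baseline, will be summarised by group, with one record per subject because the scale covers both eyes. At Day 8 and Day 30 the lower-minus-upper mean difference adjusted for baseline VAS (linear model) will be shown with its 95% CI as a descriptive estimate, without hypothesis testing.

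The text names severity because Appendix 3 asks for both severity and frequency. For any subject with two study eyes, the SAP should also say which operation's visits supply the single record. If the sponsor wants no model at all, change from baseline by group is the minimum, accepting that it is less precise than raw levels when r is below 0.5.

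The cost is a short text change and one small model per visit in an otherwise purely descriptive plan. No new visit or measurement is needed. Baseline adjustment does not make the VAS eye-specific; that limit remains.
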